5.2.1 Intent-to-Treat Population (ITT)

Will comprise any patient that is enrolled to the study and receives a dose of pembrolizumab and birinapant. Note that the ITT population can be considered equivalent to the FAS population, which is also the safety population, as no randomization is done in this study.

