5.2.3 Safety Population

Will be the same as the ITT population.

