5.3 General Principles for Presenting Study Data

All statistical analyses will be performed at SDS using SAS® (Version 9.3 or higher, SAS Institute Inc., Cary, NC, USA). All statistical analyses will be performed after this SAP is finalised and approved and the study database is locked.

Continuous data will be summarized using descriptive statistics where the following parameters will be reported:

- Number of observations (n),
- Mean,
- Median,
- Standard deviation (SD),

- Range (Min, Max)

Categorical data will be presented as the number and percentage of patients.

Time to event endpoints defined in Section 4.2.3 (e.g. duration of response, OS and time to iCPD) will be analysed using Kaplan-Meier methods taking censoring into account. The Kaplan-Meier plot and corresponding estimate of the median value with 95% confidence interval will be reported.

All tests will be one-sided and performed at the 5% significance level. When reporting the results of significance tests, p-values will be reported together with 2-sided 90% confidence intervals.

Throughout the report, the number of decimal places given for the summary statistics; mean, STD, confidence interval and median values will exceed that of the source data by one. Minimum and maximum will have the same number of decimal places as the source data. For relative frequencies, integer with one decimal and %-sign will be presented and for p-values four (three) decimals will be reported.

Percentages will be based on number of patients with data at a certain time point with the exception of presentations of medical history, medications and AEs where the percentages will be based on the number of patients in the study population.

In general, all data will be listed, sorted by phase of study, cohort and patient, and when appropriate by cycle within patient. All summary tables will be structured with a column for cohort and will be annotated with the total population size relevant to that table/cohort, including any missing observations. Summary tables will include summaries for visits for Cycle 1 (Screening, Day 1 pre dose, Day 1 post dose, Day 8 pre dose, Day 8 post dose and Day 22 End of Cycle 1 as appropriate) whereas subsequent cycles will be summarized with summary statistics for the minimum and maximum observed value during the subsequent cycles.

The two phases of the study will be summarized separately. In addition, cohorts from phase 1 and phase 2 may be combined and summarized if appropriate.

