5.6.5 Sensitivity Analyses

A sensitivity analysis of the primary endpoint will be conducted if there are patients that are wrongly included into the study and receives a dose of pembrolizumab and birinapant. In that case, the primary efficacy analysis will be repeated when those patients are excluded from the efficacy evaluable population, for the cohorts it concerns, as a sensitivity analysis. Also other major protocol deviations may be considered in this sensitivity analysis.

5.7 *Safety Analyses*

No formal statistical analyses will be performed, although descriptive summaries for continuous data and for categorical data will be provided in accordance with Section 5.3 if other not stated. Complete listings of all patient safety evaluations will be provided to support each summary table.

All presentations will be based on the safety analysis set.

5.7.1 *Adverse Events*

Adverse Events (AEs) will be coded by system organ class (SOC), preferred term (PT) and Verbatim name using MedDRA Version 20.0

All AEs will be listed whereas the treatment emergent AEs (TEAEs), i.e. any AE with onset or worsening on or after the first dose of any IMP and within 30 days after the last dose of IMP, will be summarized as follows. The number of TEAEs, as well as the number and percentage of patients reporting any TEAE will be summarised for Cycle 1, subsequent cycles and Safety follow-up by cohort. Separate summary tables will be produced for the following:

1. TEAEs related to IMP by Verbatim names
2. TEAEs related to IMP by SOC and PT
3. TEAEs not related to IMP by Verbatim name
4. TEAEs not related to IMP by SOC and PT
5. Serious Adverse Events (SAEs) by Verbatim name
6. SAEs by SOC and PT.
7. TEAEs related to IMP by AE grade
8. TEAEs not related to IMP by AE grade

AEs leading to withdrawals or death will be presented by cohort.

All percentages will be based on the number of patients in the safety set.

5.7.2 *Clinical Laboratory Tests*

All laboratory parameters for individual patients will be listed and patients with abnormal values (out of normal range reported by the laboratory) and with clinically significant abnormalities (according to the Investigator's criteria) will be flagged.

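### TEAE percentages for later periods are divided by all treated patients, so they understate incidence among the patients exposed in those periods

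*SAP*

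**What the plan says.** SAP 5.7.1 splits the TEAE tables by period: "the number and percentage of patients reporting any TEAE will be summarised for Cycle 1, subsequent cycles and Safety follow-up by cohort". The same section then sets one denominator for all of them: "All percentages will be based on the number of patients in the safety set".

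SAP 5.3 shows that this is deliberate. Its general rule bases percentages on the patients with data at the time point. It then makes an exception for medical history, "medications and AEs where the percentages will be based on the number of patients in the study population". Tables have cohort columns, each "annotated with the total population size relevant to that table/cohort, including any missing observations", so the denominator is the safety set of the cohort in question.

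SAP 5.2.3 defines the safety population by reference: "Will be the same as the ITT population". The ITT definition in SAP 5.2.1 reads: "Will comprise any patient that is enrolled to the study and receives a dose of pembrolizumab and birinapant". Neither requires a patient to reach Cycle 2 or to end treatment.

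Neither SAP 5.7.1 nor Protocol 12.6 plans an at-risk denominator, an exposure-adjusted rate or a time-to-onset analysis for adverse events.

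**The concern.** A reader takes a column labelled subsequent cycles as describing what happened to patients treated in those cycles. A patient who stopped after Cycle 1 cannot contribute an event there but still counts in the denominator as event-free. The same holds in the follow-up column for a patient still on treatment when the data are summarised. In both columns the effect can only lower the percentage relative to incidence among those at risk.

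This matters because incidence and severity of adverse events is a primary endpoint in dose escalation (Protocol 3.4.1.1) and in the various solid tumors cohort (Protocol 3.4.2.1), and a secondary endpoint in the other three cohorts (Protocol 3.4.2.2). Stopping early can itself be caused by toxicity. Under Protocol 5.4, cytokine release syndrome above Grade 2 in Cycle 1 ends both study drugs permanently. Those patients remain in the later denominators, so more stopping for toxicity in Cycle 1 lowers the later percentages mechanically.

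The report would also be uneven. Physical examination percentages over time (SAP 5.7.3) follow the general data-at-time-point rule, and the adverse event tables do not.

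**Working it through.** The documents state no adverse event rate, no rate of continuation to Cycle 2 and no rate of entry to follow-up, so the plan has no figure to reproduce. The relation is pure arithmetic.

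**Inputs from the documents**
- Periods: Cycle 1, subsequent cycles (pooled), safety follow-up (SAP 5.7.1).
- Denominator: the cohort's safety set, N (SAP 5.7.1, 5.3).
- Expansion cohorts: 28 colorectal, 27 ovarian, 26 cervical, 30 various solid tumors, total 111 (SAP 3.1.2).
- Escalation dose groups: 3 to 6 patients (SAP 3.3.1.1).
- TEAE window: first dose to 30 days after the last dose (SAP 5.7.1).

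**Formula**

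Let x be the patients with an event in the period, n the patients who entered it, and f = n/N.

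Reported proportion = x/N = (x/n) × (n/N) = at-risk proportion × f.

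Relative shortfall = 1 - f.

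For Cycle 1, f = 1, because every safety-set patient has been dosed. For the later columns, f is below 1 as soon as one patient has not entered the period.

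**Size, with f assumed**

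| f | 30% at risk is shown as | Relative shortfall |
|---|---|---|
| 0.95 | 0.30 × 0.95 = 28.5% | 5% |
| 0.90 | 0.30 × 0.90 = 27.0% | 10% |
| 0.80 | 0.30 × 0.80 = 24.0% | 20% |
| 0.70 | 0.30 × 0.70 = 21.0% | 30% |

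**In cohort terms, with assumed counts**
- Colorectal, N = 28, 22 start Cycle 2, 7 have an event: 7/28 = 25.0% under the SAP rule, 7/22 = 31.8% of those at risk.
- Various solid tumors, N = 30, 24 start Cycle 2, 7 have an event: 7/30 = 23.3% against 7/24 = 29.2%.
- All expansion patients, N = 111, 89 start Cycle 2, 27 have an event: 27/111 = 24.3% against 27/89 = 30.3%.

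**Escalation dose groups**

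If one patient in a group of size N does not reach Cycle 2, f = (N - 1)/N and the shortfall is 1/N. That is 1/6 for a group of 6 and 1/3 for a group of 3. For example, 1 of 2 at risk (50%) is shown as 1 of 3 (33.3%).

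**Where f is likely to fall**

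For subsequent cycles, all later cycles are pooled, so the relevant loss is only that before the first dose of Cycle 2. Eligibility requires ECOG 0 or 1 and a life expectancy above 12 weeks (Protocol 4.1), and the first scan is at week 9 (Protocol 9.1.3). Loss before Cycle 2 may therefore be modest.

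For safety follow-up, f depends on how many patients have ended treatment when the table is run. Treatment may last 35 cycles (Protocol 3.3). Protocol 19 allows ad hoc analyses of preliminary data, handled as in the SAP, and in those, patients still on treatment would count as event-free in this column.

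**The case against.** The strongest reply is that the percentage is not wrong. The protocol's endpoint is the incidence of adverse events in patients who receive the combination, and the safety set is exactly those patients. The SAP discloses the denominator twice and never defines an at-risk proportion as its target. This stands: x/N is a valid crude share of treated patients. It falls short only as a description of incidence among patients exposed in the period, which is how a period column is naturally read.

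It can also be said that much of the information is recoverable. The tables give patient counts, all adverse events are listed, and SAP 5.5.6 summarises the number of cycles started by cohort. No test or escalation rule uses these percentages. This is fair, and it limits the consequence. But a reader should not have to rebuild the denominator of a primary safety table from an exposure table.

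Four stronger readings are tempting, and the documents do not support them.

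- **Toxicity would appear to fall over time.** Cycle 1 lasts 21 days, the second column pools up to 34 further cycles, and follow-up is 30 days. Proportions over such unequal periods cannot show a trend under either denominator. The long pooled period pushes the second column up, so the net direction is unknown.
- **Late immune-related events would be hidden.** Protocol 5.5 says such events may arise months after the last dose, but a TEAE must begin or worsen within 30 days of it. Later onsets lie outside every column, whatever the denominator.
- **One early stopper would cut a percentage by a fifth in the five-patient tumor groups.** The tables are by cohort, the various solid tumors cohort is one group of 30, and no subgroup analyses are planned (SAP 5.4.5).
- **Follow-up percentages would be roughly halved.** This needs only about half the patients to have entered follow-up. SAP 5.1 places the final analysis after database lock, and Protocol 6.3 has all patients return 30 days after the last dose. Nothing in the documents supports so low a fraction.

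**Conclusion.** The point holds in a limited form. For the subsequent-cycles and safety follow-up columns, the SAP's denominator includes patients who could not have had an event in the period. The reported percentage is then below the incidence among exposed patients by a relative 1 - f. Cycle 1 is unaffected.

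The size cannot be fixed from the documents. At assumed fractions of 0.95 to 0.80, a 30% incidence at risk loses 1.5 to 6 percentage points. In escalation dose groups of 3 to 6, a single patient not reaching Cycle 2 costs a sixth to a third of the figure. The algebra rests on no assumption; the illustrations rest on the assumed f and the assumed 30%.

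The conclusion concerns how period percentages are labelled and read. It does not show that the trial would report declining toxicity, it does not concern events more than 30 days after the last dose, and it does not touch the response-rate analyses. It is worth correcting because the endpoint is primary in escalation and in the various solid tumors cohort.

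**What to change.** In SAP 5.7.1, replace the single denominator with one per column:

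- **Cycle 1, an overall column, and adverse events leading to withdrawal or death:** the cohort's safety set, as now.
- **Subsequent cycles:** safety-set patients with at least one dose in Cycle 2 or later.
- **Safety follow-up:** all safety-set patients who have permanently stopped study treatment, whether or not they attended the follow-up visit. Requiring a follow-up observation would select the patients who came back or reported, and could overstate incidence.

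Print the resulting N in each column, and amend the adverse event exception in SAP 5.3 to match.

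The cost is a short SAP edit and some programming. No new data are needed, since dosing by cycle is already recorded, and Protocol 12.6 sets no denominator that would conflict. The downside is that denominators differ between columns, so the columns no longer share a base, and later-period percentages become somewhat higher. The change does not make periods of different length comparable.

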5.7.4 Vital Signs

Vital signs will be summarized regarding observed values and change from baseline in accordance with Section 5.3 by cancer cohort and in total over cohorts.

In case several measurements are taken for the same planned sample time, average values will be used.

5.7.5 Electrocardiogram

ECG results will be summarized regarding observed values, change from baseline values and findings (normal, abnormal not clinically significant and abnormal clinical significant) in accordance with Section 5.3 by cancer cohort.

If one of the measurements within a triplicate ECGs is classified as abnormal the value for that visit is classified as abnormal.

5.8 Pharmacokinetic Analyses

The raw PK data (actual drug concentrations) will be summarized in accordance with Section 5.3. The PK data will be summarized by dose and (nominal) sampling time in the dose escalation phase of the study. Whereas in the dose expansion phase, the data will be summarized by cohort and scheduled (nominal) sampling time and over cohorts by scheduled (nominal) sampling time, as appropriate. A sample with actual sample time outside the acceptable time window will not be included in the summary statistics, but will appear in the listings.

Concentration-time data that are below lower limit of quantification (LLOQ) will be treated as zero for PK analysis. The number (and the percentage) of samples below LLOQ will be shown in the summary tables.

Individual graphs on PK (plasma concentration versus actual time point) will be reported for each patient separately, and summarized by cohort/dose group.

The PK analysis will be performed on the PK population set.

Population PK modeling may also be applied to analyze the PK data and will, in that case, be reported separately.

5.9 Changes to Planned Analysis

The statistical analysis of the primary endpoint has been supplemented with how the analysis will be done in case of the number of patients evaluable for efficacy differs from the planned number of patients in the Simon's design.

6. References

BPT-201 v4.0/incl amendment 03, final version dated 18 January 2018.

Imaging Review Charter for BPT-201, MEDIAN Technologies, 7 February 2018.

Simon R. Optimal two-stage designs for phase II clinical trials. *Controlled Clinical Trials.* 1989; 10(1):1–10. [PubMed: 2702835]

Statistical Principles for Clinical Trials (ICH Topic E 9). EMEA. September 1998, CPMP/ICH/363/96.

7. Appendix 1

Table 5 Schedule of Study Procedures and Assessments

Study Procedures	Screening (Within 28 Days of Cycle 1 Day 1)	Cycle 1			Subsequent Cycles		End of the Third Week of Every Third 21- Day Cycle	Every six weeks	Every 12 weeks	Follow up		
		Day 1	Day 2	Day 8	Day 1	Day 8				Safety Follow up Visit (30 Days After Study Drug Discontinuation)	Progressive Disease/ Study Drug Discontinuation ²⁰	Overall Survival Follow-up ²¹
Visit Window				± 2 Days		± 2 Days	± 3 Days			+7 Days	± 3 Days	
Informed Consent	X											
Inclusion/ Exclusion Criteria	X											
Demographics	X											
Medical History and Disease Characteristics ¹	X											
ECOG Performance Status	X	X			X					X	X	
Serology ² (HSV, VZV)	X											
Review Prior/ Concomitant Medications	X	X		X	X	X				X		
Measurement of Vital Signs ³	X	X		X	X	X				X		
Physical Examination	X	X			X					X		
Weight and Height ⁴	X	X			X							

Study Procedures	Screening (Within 28 Days of Cycle 1 Day 1)	Cycle 1			Subsequent Cycles		End of the Third Week of Every Third 21- Day Cycle	Every six weeks	Every 12 weeks	Follow up		
		Day 1	Day 2	Day 8	Day 1	Day 8				Safety Follow up Visit (30 Days After Study Drug Discontinuation)	Progressive Disease/ Study Drug Discontinuation ²⁰	Overall Survival Follow-up ²¹
Visit Window				± 2 Days		± 2 Days	± 3 Days			+7 Days	± 3 Days	
BSA Calculation ⁵		X			X							
Serum Chemistry ⁶	X	X		X	X	X				X	X	
Hematology ⁷	X	X		X	X	X				X	X	
Urinalysis ⁸	X	X			X					X		
Hepatitis C antibody	X											
CA-125 (Ovarian Cancer patients only)	X	X			X					X		
CEA (CRC patients only)	X								X	X		
MSI for CRC patients ¹⁶	X											
Pregnancy Test ⁹	X	X			X					X		
12-Lead Electrocardiogram	X	X		X	X	X				X		
Adverse Events ¹⁰		X	X	X	X	X				X		
Administration of pembrolizumab ¹¹		X			X							
Administration of NSAIDs ¹²		X		X	X	X						
Administration of birinapant ¹³		X		X	X	X						
Pharmacodynamic Blood Sampling ¹⁴		X	X	X								

Study Procedures	Screening (Within 28 Days of Cycle 1 Day 1)	Cycle 1			Subsequent Cycles		End of the Third Week of Every Third 21- Day Cycle	Every six weeks	Every 12 weeks	Follow up		
		Day 1	Day 2	Day 8	Day 1	Day 8				Safety Follow up Visit (30 Days After Study Drug Discontinuation)	Progressive Disease/ Study Drug Discontinuation ²⁰	Overall Survival Follow-up ²¹
Visit Window				± 2 Days		± 2 Days	± 3 Days			+7 Days	± 3 Days	
CD3+, CD4+, CD8+, CD19+, ANC, ALC Blood Sampling		X ¹⁵		X ¹⁷								
Archival Tumor Tissue Sample for Pharmacodynamic Analysis ¹⁸	X											
Optional Tumor Biopsy Sample for Pharmacodynamic Analysis	X ¹⁸				X ¹⁸							
Radiological Tumor Assessment ¹⁹	X						X				X	
ANC and ALC			X									
Survival Status												X
Pharmacokinetic Blood Sampling ²²		X	X	X								
Thyroid testing ⁶	X							X				

- 1 Medical history and disease characteristics should include the date of the initial cancer diagnosis, a listing of relevant past and current diseases, and the details of active disease.
- 2 For those patients that may develop cranial nerve palsy, a second sample will be collected at the time of the event to assess for HSV (herpes simplex virus) and VZV (varicella zoster virus) viral titers.
- 3 Vital signs will be collected at Screening and on Days 1, and 8 of every 21-day cycle and will include blood pressure, respiration rate, heart rate, and body temperature. Vital signs should be collected pre- and post-administration of pembrolizumab, and; pre- and post-administration of birinapant).
- 4 Height and weight is to be measured at screening. Weight should be measured for each BSA calculation.
- 5 If a patient's BSA is > 2.5, then 2.5 will be used to calculate the patient's study-drug dose. If the patient's body weight has changed > 10% from that used to calculate the prior BSA, the BSA will be recalculated and the dose adjusted.
- 6 Serum chemistry will be performed at screening (within 10 days of Cycle 1 Day 1) and on Days 1 and 8 of every cycle beginning with Cycle 1 Day 1. Chemistry panel is to include the following parameters: lipase, amylase, albumin, total protein, blood glucose (non-fasting), sodium, potassium, chloride, bicarbonate, magnesium, calcium, blood urea nitrogen (BUN), creatinine, AST, ALT, alkaline phosphatase (ALP), total bilirubin, direct bilirubin, lactate dehydrogenase (LDH), gamma glutamyltransferase (GGT), and phosphate. If screening

- chemistry is performed within 72 hours of Cycle 1 Day 1, the sample does not need to be repeated. Thyroid function testing includes triiodothyronine (T3) or free triiodothyronine (FT3), Thyroxine (T4) or free thyroxine (FT4), and TSH
- 7 Hematology will include CBC and differentials. Hematology will be performed at screening (within 10 days of Cycle 1 Day1) and on Days 1 and 8 of every cycle beginning with Cycle 1 Day 1. If screening hematology is performed within 72 hours of Cycle 1 Day 1, the sample does not need to be repeated
- 8 Urinalysis will be performed at screening and on Day 1 of every 21-day cycle. If screening urinalysis is performed within 72 hours of Cycle 1 Day 1, the sample does not need to be repeated
- 9 For women of child bearing potential, a serum pregnancy test must be performed at screening only. Urine or serum pregnancy tests must be done within 72 hours before the first dose of study drug. A urine pregnancy test can be performed at all other study visits. Monthly pregnancy testing should be conducted as per local regulations where applicable.
- 10 The adverse event reporting period is from the time the patient signs consent until 30 days after study-drug discontinuation. Adverse events that lead to study-drug discontinuation should be followed until resolution or stabilization.
- 11 Pembrolizumab 200 mg will be administered first on Day 1 of each 21-day cycle.
- 12 All patients will be required to be administered All patients will be required to be administered 800 mg of ibuprofen (or equipotent and equivalent alternative NSAID) prior to administration of birinapant on Day 1 and Day 8 as prophylaxis for possible events of cranial nerve palsy associated with the administration of birinapant.
- 13 Birinapant will be administered 30 minutes (+10 minutes) after pembrolizumab on Day 1 and by itself on Day 8 of each 21-day cycle.
- 14 Pharmacodynamic blood samples will be collected from all patients in Cycle 1. These samples will be sent to a central laboratory for analysis.
- Day 1: prior to pembrolizumab (sample 1) and 4 hours post-birinapant dose (sample 2)
 - Day 2: 24 hours post-birinapant dose (from Day 1) (sample 3)
 - Day 8: prior to birinapant (sample 4) and 4 hours post-birinapant dose (sample 5)
- 15 A peripheral blood sample will be collected to assess for CD3⁺, CD4⁺, CD8⁺, CD19⁺, ANC and ALC on cycle 1 day 1 prior to the pembrolizumab infusion A CBC is required prior to dosing. This sample will be analyzed locally.
- 16 MSI testing for CRC patients done at local laboratory. Results from an historical sample can be used if done within 24 months of C1D1
- 17 A peripheral blood sample will be collected to assess for CD3⁺, CD4⁺, CD8⁺, CD19⁺, ANC and ALC on cycle 1 day 8 4 hours after the completion of the birinapant infusion. A CBC is required prior to dosing. This sample will be analyzed locally.
- 18 Archival tumor tissue sample for biomarkers should be obtained during screening (pre-dose; paraffin embedded archival); if no archival sample is available, a fresh biopsy, though not required, may be obtained. A subsequent second optional fresh tumor biopsy may be requested at any time during Cycle 2 (time of sampling post-dose will be recorded) or after to assess the pharmacodynamics of birinapant and pembrolizumab in this patient population. For further information, consult the laboratory manual.
- 19 All patients will be required to have a CT scan of their chest, abdomen and pelvis during screening. MRIs will be allowed but the same radiological modality must be used at each repeat assessment. Repeat radiological assessments will be performed every 9 weeks (last week of every 3rd cycle). In the event of a response, a confirmatory scan must be performed 4 weeks following initial assessment of response. All radiological assessments will be reviewed according to both RECIST v 1.1 and iRECIST criteria.
- 20 Patients who discontinue from study treatment due to reasons other than disease progression will need to be followed every 30 days until documentation of disease progression or initiation of a new therapy for their disease. Once disease progression is documented or new therapy is initiated the patient will move into the survival follow up stage of the protocol.
- 21 Patients will be contacted by telephone every 3 months after last study-drug treatment for survival information and subsequent therapy information
- 22 Pharmacokinetic blood samples will be collected from all patients in Cycle 1. These samples will be sent to a bioanalytical laboratory for analysis.
- Day 1: 4 hours after completion of birinapant infusion (sample 2)
 - Day 2: 24 hours after completion of birinapant infusion (from Day 1) (sample 3)
 - Day 8: prior to birinapant (sample 4) and 4 hours after completion of birinapant infusion (sample 5)
